1	PIs ¹	Medical claim with an NDC, HCPCS, generic name or CPT code in the IP, non-IP, or pharmacy setting for bortezomib, carfilzomib, or ixazomib (dichotomous)	MM diagnosis to 1 day prior to index date Index date to the end of follow-up
1	IMiDs ¹	Medical claim with an NDC code or generic name in the non-IP or pharmacy setting for lenalidomide, thalidomide, or pomalidomide (dichotomous)	MM diagnosis to 1 day prior to index date Index date to the end of follow-up
1	Steroids ¹	Medical claim with an NDC, HCPCS, generic name or CPT code in the IP, non-IP, or pharmacy setting for dexamethasone, methylprednisolone, prednisone, or prednisolone (dichotomous)	MM diagnosis to 1 day prior to index date Index date to the end of follow-up
1	MAbs ¹	Medical claim with an NDC, HCPCS, generic name or CPT code in the IP, non-IP, or pharmacy setting for daratumumab, isatuximab, or elotuzumab (dichotomous)	MM diagnosis to 1 day prior to index date Index date to the end of follow-up
1	Chemotherapies ¹	Medical claim with an NDC, HCPCS, generic name or CPT code in the IP, non-IP, or pharmacy setting for	MM diagnosis to 1 day prior to index date

Objective	Variable	Definition	Assessment Period(s)
		doxorubicin hydrochloride, melphalan, bendamustine, cyclophosphamide, etoposide, or cisplatin (dichotomous)	Index date to the end of follow-up
1	Small molecule inhibitors ¹	Medical claim with an NDC, HCPCS, generic name or CPT code in the IP, non-IP, or pharmacy setting for venetoclax (dichotomous)	MM diagnosis to 1 day before index date Index date to the end of follow-up
1	Nuclear export inhibitors ¹	Medical claim with an NDC, HCPCS, generic name or CPT code in the IP, non-IP, or pharmacy setting for selinexor (dichotomous)	MM diagnosis to 1 day before index date Index date to the end of follow-up
1	Antivirals ¹	Medical claim with an NDC, HCPCS, generic name or CPT code in the IP, non-IP, or pharmacy setting for antiviral medications (dichotomous)	14 days prior to index date to 1 day prior to index date Index date to the end of follow-up
1	Antibiotics ¹	Medical claim with an NDC, HCPCS, generic name or CPT code in the IP, non-IP, or pharmacy setting for antibiotic medications (dichotomous)	14 days prior to index date to 1 day prior to index date Index date to the end of follow-up

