		PJP Hepatitis C Hepatitis B Other infectious hepatitis Helicobacter pylori Candida esophagitis Urinary tract infection	
Effectiveness			
Exploratory Obj 2	OS	Time (in months) from index date until date of death (continuous)	Index date until censor See Section 9.7.7 for censoring criteria
Exploratory Obj 2	TTNT/D	Time (in months) from index date until the date of the next treatment (CAR-T, BsABs, bendamustine or belantamab) or death (continuous)	Index date until censor See Section 9.7.7 for censoring criteria

1. Variable will be measured as incident and prevalent. Incident cases have 30-day washout period applied
2. Variable will be measured as incident and prevalent. Incident cases have 60-day washout period applied
3. Variable will be measured as incident and prevalent. Incident cases have 14-day washout period applied

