9.7.6. Tolerability

The prevalence and incidence for each AE (Table 3) will be estimated. All prevalence and incidence estimate will be reported as a percent with corresponding 95% CIs.

$$\text{Prevalence} = \left(\frac{\text{Number of patients with an event}}{\text{Total number of patients in the cohort}} \right) \times 100$$

For the incidence analysis, only patients who did not have the event in prior to their index date will be excluded. The length of the washout is dependent on the outcome (see Table 3).

$$\text{Incidence} = \left(\frac{\text{Number of patients with an event who did not have an event at baseline}}{\text{Total number of patients in the cohort}} \right) \times 100$$

Patients will be assessed over two time periods: from the index date until 14 days or 90 days after their last administration of the index medication.

Additionally, the time to infection onset will be assessed using unadjusted Kaplan-Meier methods. The median time to event in days will be reported along with the IQR. The 95% CIs for the median time to event will be calculated using log-log transformation.

Patients will be censored at the earliest of death, the end of continuous closed-claim coverage, the latest data at the time of the specified analysis, or next treatment (CAR-T, BsABs, bendamustine or belantamab).

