9.7.7. Overall Survival and Time to Next Treatment

OS and TTNT/D will be assessed using unadjusted Kaplan-Meier methods. The median time to event in months will be reported along with the IQR. The 95% CIs for the median time to event will be calculated using log-log transformation. Results will be depicted graphically by Kaplan-Meier curves, and the percentage of patients who reached the outcome and censored patients will also be reported.

OS will be assessed as the time in months from index date to date of death. Patients without an event will be censored at the earliest of the end of continuous closed-claim coverage or the end of data.

TTNT/D will be assessed as the time in months from index date until switch a new treatment or death. Patients without an event will be censored at the earliest of the end of continuous closed-claim coverage, or the end of data.

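### TTNT/D counts only CAR-T, bispecifics, bendamustine and belantamab as next treatment, so patients who switch to other listed myeloma drugs stay event-free and the endpoint runs long

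*Protocol*

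**What the plan says.** Section 9.3, Table 3 fixes the endpoint with a closed list: "Time (in months) from index date until the date of the next treatment (CAR-T, BsABs, bendamustine or belantamab) or death (continuous". Section 9.7.7 describes the same endpoint without a list: "TTNT/D will be assessed as the time in months from index date until switch a new treatment or death". Censoring in 9.7.7 is stated for OS as "Patients without an event will be censored at the earliest of the end of continuous closed-claim coverage or the end of data" and repeated for TTNT/D with no change of substance. Starting a drug outside the list therefore neither ends nor censors follow-up.

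Table 2 names many other antimyeloma drugs:

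- proteasome inhibitors: "bortezomib, carfilzomib, or ixazomib (dichotomous"
- IMiDs: "lenalidomide, thalidomide, or pomalidomide (dichotomous"
- monoclonal antibodies: "daratumumab, isatuximab, or elotuzumab (dichotomous"
- chemotherapies: "doxorubicin hydrochloride, melphalan, bendamustine, cyclophosphamide, etoposide, or cisplatin (dichotomous"
- venetoclax and selinexor

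The footnote to Table 2 marks these classes as measured after index as well as at baseline. Annex 2 also gives them a role in the HCRU outcomes, where treatment for MM makes a claim myeloma-related.

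Section 9.7.6 reuses the short list to censor adverse-event and time-to-infection follow-up: "or next treatment (CAR-T, BsABs, bendamustine or belantamab".

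**The concern.** A post-index claim for, say, carfilzomib or selinexor is myeloma treatment when resource use is counted, but not a next treatment when TTNT/D is counted. The two descriptions of the endpoint also differ: one has a closed list, the other refers to any new treatment. Section 9.8 says the protocol will be followed strictly, so the choice between them decides the result.

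TTNT/D is one of two effectiveness endpoints, and section 9.9 says that progression-free survival and response are not available in these data. A TTNT/D that passes over switches to most available drug classes does not measure what its name says. In the tolerability analysis, infections and other events that arise under an unlisted next regimen would be reported as events on the index drug.

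**Working it through.** **No stated figure to reproduce.** The protocol gives no expected TTNT/D median, event count or off-list share.

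**Step 1: how much of the treatment list is left out.** I counted the antimyeloma agents in Table 2 plus the other BCMA bispecific, leaving out steroids, transplant and the index drug.

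- Counted as next treatment: two CAR-T products, belantamab, talquetamab, the other BCMA bispecific and bendamustine = 6.
- Not counted: 3 proteasome inhibitors + 3 IMiDs + 3 monoclonal antibodies + 5 of 6 chemotherapies + venetoclax + selinexor = 16.
- Share not counted: 16 / (16 + 6) = 16/22 = 73% of agents. This is a share of drugs, not of patients.

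**Step 2: direction.** The time to the first event from a subset is never shorter than the time to the first event from the full set. With the same censoring times, the short-list Kaplan-Meier curve lies on or above the full-list curve. The two coincide only if no first event is an off-list switch.

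**Step 3: size, under assumptions.** Let m be the median when every switch counts and λ = ln 2 / m the total hazard. Let s be the share of first events that are off-list switches. Let r be the factor by which the hazard of a listed treatment or death changes after such a switch, so that h = r(1 − s)λ. The short-list survival curve is

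S(t) = exp(−λt) + sλ [exp(−ht) − exp(−λt)] / (λ − h),

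and the reported median solves S(t) = 0.5. For r = 1 this reduces to m / (1 − s). With m = 6.0 months as an example:

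| s | r = 1 | r = 2 | r = 3 |
|---|---|---|---|
| 0% | 6.0 | 6.0 | 6.0 |
| 10% | 6.67 (+11%) | 6.47 (+8%) | 6.36 (+6%) |
| 20% | 7.50 (+25%) | 7.05 (+18%) | 6.79 (+13%) |
| 30% | 8.57 (+43%) | 7.76 (+29%) | 7.32 (+22%) |
| 50% | 12.0 (+100%) | 9.92 (+65%) | 8.93 (+49%) |

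The percentages do not depend on m. Check at s = 20%, r = 1: 6.0 / 0.8 = 7.5.

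**Step 4: where else the list bites.**

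- *Adverse events (9.7.6).* Two windows are planned, to 14 and to 90 days after the last administration. The longer one adds 90 − 14 = 76 days, and the short list is its only treatment-switch cut-off.
- *Time to infection onset (Table 3, 9.7.6).* It runs from index to censoring, with the same list as the only treatment-switch rule.
- *TTD (Table 3).* An 8-week gap in the index drug already ends it.
- *Dosing outcomes and RAI (9.7.2, 9.7.3).* These count index-drug claims or stop at the last administration.
- *HCRU (9.7.5).* Baseline, step-up and index-to-last-dose contain no time after the last dose. Only the window ending at discontinuation might, for at most about 8 weeks.

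**The case against.** The list is applied consistently: it is the same in Table 3 for TTD and TTNT/D and in sections 9.7.2, 9.7.5 and 9.7.6. The open wording in 9.7.7 can be read as shorthand for the Table 3 variable. The protocol defines no line-of-therapy algorithm, and claims do not easily separate an add-on drug from a switch, so a short list of unambiguous switches is a defensible choice. Off-list use is not hidden, because Table 2 tabulates those classes after index. TTNT/D is exploratory and descriptive.

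Much of this stands as a limit on weight. It does not remove the problem: the protocol gives no reason for the restriction, section 9.9 does not list it as a limitation, and a separate table of off-list use does not correct the curve.

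Three stronger readings are tempting and are not supported.

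- A reader might infer that exposure, RAI, TTD and cost results are all contaminated. Step 4 shows that they are little affected, with one HCRU window as the possible exception.
- A reader might infer a biased comparison of elranatamab with teclistamab. Section 9.7 plans no formal comparison, and the documents hold no data on differing access to the listed drugs.
- A reader might call TTNT/D the only stand-in for loss of disease control. TTD, with its gap rule, also reflects stopping of the index drug.

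**Conclusion.** The point holds for TTNT/D first, and for the 90-day adverse-event window and time to infection onset second. The direction is certain once any patient's first event is an off-list switch. The size is not known. At an assumed off-list share of 20% the median is overstated by about 13% (later hazard tripled) to 25% (later hazard unchanged); at 10% the range is 6% to 11%. These figures rest on constant hazards and on r between 1 and 3; a hazard that fell after the switch would give a larger overstatement. Nothing in the protocol shows which share applies, so the table is an illustration and not an estimate. The 14-day adverse-event window limits the leakage into safety results but does not help time to infection.

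**What to change.** Reconcile Table 3 and section 9.7.7 with one definition. Next treatment is the earliest claim, after the last index-drug administration, for any antimyeloma agent named in Table 2 other than steroids, where the index drug has been discontinued under the protocol's existing 8-week gap. CAR-T or another bispecific counts whenever it occurs. State whether bendamustine and belantamab follow the general rule, and how to treat patients whose follow-up ends before 8 weeks have passed.

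Use the agents named in Table 2. The Annex 2 chemotherapy list should not be taken as it stands, because it adds methotrexate and cytarabine.

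Apply the same rule to adverse-event and time-to-infection censoring in 9.7.6. Tabulate the share of first events that are off-list switches. Keep the present short list as a sensitivity analysis.

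The cost is a change of definition and some reprogramming; Annex 2 already covers the drug classes, and result refreshes are already planned. Median TTNT/D is likely to be shorter. Some bridging or non-myeloma use will be misclassified as a switch, and the short-list analysis shows how far that could matter. Because the rule depends on later claims, a patient's event status may change between data refreshes, and the report should say so.

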9.2. Setting

This study will evaluate adult patients with RRMM who initiate elranatamab. Patients will enter (i.e., index) on the first observed elranatamab claim between 14 August 2023 and the end of data (defined as the latest data at the time of the specified analysis). Limited eligibility criteria will be applied.

Study Period: Start of data availability (01 January 2016) to the end of data

MM diagnosis window: Start of data availability (01 January 2016) to index date

Index date: First elranatamab claim after initial MM diagnosis

Observability: At least 180 days of continuous closed-claims medical and pharmacy enrollment prior to index (inclusive)

[figure not shown]
Baseline period for MM-related treatments and MM-related comorbidities: MM diagnosis to one day prior to index date (unless otherwise specified)

CCI and baseline HCRU assessment window: 180 days prior to index date to index date.

Follow-up: Index date until death, the earliest of the end of data, or end of continuous enrollment (unless otherwise noted). Alternative censoring criteria will be applied for certain outcomes (such as OS, TTD, and TTNT/D); see [Section 9.7](#) for more details.

Figure 1 reflects the time periods of interest in the study cohort.

Figure 1. Study Schematic for Patients Receiving Elranatamab

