9.2.1. Inclusion Criteria

Patients must meet all of the following inclusion criteria to be eligible for inclusion in the study:

1. Index date: First observed prescription claim or medical claim for elranatamab in the dataset (14 August 2023 to the end of data)
2. Age 18 or older on index date

3. Diagnosis of RRMM (defined as MM) any time prior to index date
4. At least 180 days of continuous closed-claims medical and pharmacy enrollment prior to index (inclusive)

For the exploratory cohort of patients receiving teclistamab, patients will be required to meet the same inclusion criteria as those receiving elranatamab. The only difference is that patients will index on their first teclistamab claim within the same time window (14 August 2023 to the end of data).

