Exploratory Obj 1	Hypophosphataemia ¹	Medical claim with an ICD-10 code in the IP, non-IP, or pharmacy setting for hypophosphatemia (dichotomous)	Index date to end of follow-up, where follow-up will be based on last dose of elranatamab (eg, 14 days after last recorded dose or 90 days after last recorded dose). See Section 9.7.6 for censoring criteria

Exploratory Obj 1	Hypokalaemia ¹	Medical claim with an ICD-10 code in the IP, non-IP, or pharmacy setting for hypokalemia or event in the lab table where potassium serum is < 3.0 mmol/L (dichotomous)	Index date to end of follow-up, where follow-up will be based on last dose of elranatamab (eg, 14 days after last recorded dose or 90 days after last recorded dose). See Section 9.7.6 for censoring criteria
Exploratory Obj 1	Hepatotoxicity ¹	Medical claim with an ICD-10 code in the IP, non-IP, or pharmacy setting for hepatotoxicity (dichotomous)	Index date to end of follow-up, where follow-up will be based on last dose of elranatamab (eg, 14 days after last recorded dose or 90 days after last recorded dose). See Section 9.7.5 for censoring criteria
Exploratory Obj 1	Renal failure ²	Medical claim with an ICD-10 code in the IP, non-IP, or pharmacy setting for renal failure (dichotomous)	Index date to end of follow-up, where follow-up will be based on last dose of elranatamab (eg, 14 days after last recorded dose or 90 days after last recorded dose). See Section 9.7.6 for censoring criteria
Exploratory Obj 1	Peripheral neuropathy ¹	Medical claim with an ICD-10 code in the IP, non-IP, or pharmacy setting for peripheral neuropathy (dichotomous)	Index date to end of follow-up, where follow-up will be based on last dose of elranatamab (eg, 14 days after last recorded dose or 90 days after last recorded dose). See Section 9.7.6 for censoring criteria

Exploratory Obj 1	Arthralgia ³	Medical claim with an ICD-10 code in the IP, non-IP, or pharmacy setting for arthralgia (dichotomous)	Index date to end of follow-up, where follow-up will be based on last dose of elranatamab (eg, 14 days after last recorded dose or 90 days after last recorded dose). See Section 9.7.6 for censoring criteria
Hematologic events			

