Exploratory Obj 1	Hepatitis C ²	Medical claim with an ICD-10 code in the IP, non-IP or pharmacy setting for hepatitis C (dichotomous)	Index date to end of follow-up, where follow-up will be based on last dose of elranatamab (eg, 14 days after last recorded dose or 90 days after last recorded dose). See Section 9.7.6 for censoring criteria
Exploratory Obj 1	Hepatitis B ²	Medical claim with an ICD-10 code in the IP, non-IP or pharmacy setting for hepatitis B (dichotomous)	Index date to end of follow-up, where follow-up will be based on last dose of elranatamab (eg., 14 days after last recorded dose or 90 days after last recorded dose). See Section 9.7.6 for censoring criteria
Exploratory Obj 1	Other infectious hepatitis ²	Medical claim with an ICD-10 code in the IP, non-IP or pharmacy setting for other infectious hepatitis (dichotomous)	Index date to end of follow-up, where follow-up will be based on last dose of elranatamab (eg., 14 days after last recorded dose or 90 days after last recorded dose). See Section 9.7.6 for censoring criteria
Exploratory Obj 1	Helicobacter pylori ²	Medical claim with an ICD-10 code in the IP, non-IP or pharmacy setting for helicobacter pylori (dichotomous)	Index date to end of follow-up, where follow-up will be based on last dose of elranatamab (eg, 14 days after last

			recorded dose or 90 days after last recorded dose). See Section 9.7.6 for censoring criteria
Exploratory Obj 1	Candida esophagitis ²	Medical claim with an ICD-10 code in the IP, non-IP or pharmacy setting for candida esophagitis (dichotomous)	Index date to end of follow-up, where follow-up will be based on last dose of elranatamab (eg, 14 days after last recorded dose or 90 days after last recorded dose). See Section 9.7.6 for censoring criteria
Exploratory Obj 1	Urinary tract infection ²	Medical claim with an ICD-10 code in the IP, non-IP or pharmacy setting for a urinary tract infection (dichotomous)	Index date to end of follow-up, where follow-up will be based on last dose of elranatamab (eg, 14 days after last recorded dose or 90 days after last recorded dose). See Section 9.7.6 for censoring criteria
Exploratory Obj 1	Time to infection onset	Time in days from index date to first infection for the following infections: COVID-19 Sinusitis Bronchitis Adenoviral pneumonia Cytomegaloviral pneumonitis Pneumonia Sepsis Cytomegaloviral infection	Index date until censor See Section 9.7.6 for censoring criteria

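### Washouts of 30 and 60 days can turn long-standing neuropathy and hepatitis B/C into incident adverse events, although every patient has 180 days of look-back

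*Protocol*

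**What the plan says.** The footnotes to Table 3 (Section 9.3) set the washouts. Footnote 1, which marks peripheral neuropathy, says "Incident cases have 30-day washout period applied". Footnote 2, which marks renal failure, hepatitis B and hepatitis C, says "Incident cases have 60-day washout period applied". Section 9.7.6 takes the washout length from Table 3, and its incidence numerator counts patients with an event who had none at baseline.

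One claim is enough for an event. The neuropathy definition, for example, is "Medical claim with an ICD-10 code in the IP, non-IP, or pharmacy setting for peripheral neuropathy (dichotomous".

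Two longer look-back windows already exist:

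- Eligibility (Section 9.2.1) requires "At least 180 days of continuous closed-claims medical and pharmacy enrollment prior to index (inclusive".
- Section 9.2 defines "Baseline period for MM-related treatments and MM-related comorbidities: MM diagnosis to one day prior to index date (unless otherwise specified". Table 2 applies this window to peripheral neuropathy, to renal failure and to the any-infection variable, which includes hepatitis B and C.

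The protocol gives no reason for the 30- and 60-day lengths, and Section 9.9 does not list the resulting misclassification as a limitation.

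**The concern.** A chronic condition appears in claims only when a visit or service is billed under it. A short gap in coding does not show that the patient is free of it. Under a short washout, someone with known disease and no recent code passes as event-free, and the next code after index becomes an incident event in the safety table.

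The incidence column is the only adverse-event measure meant to isolate new events, because the prevalence formula in Section 9.7.6 makes no exclusion for prior disease. Section 7 designates the study a PASS, so readers are likely to treat incidence as the informative safety figure. For chronic conditions it would be biased upward, and prevalence cannot correct it.

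**Working it through.** The protocol has no figure to reproduce here. The check compares the windows and code lists, then illustrates the size.

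**1. Windows for the same condition**

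| Condition | Incidence washout (Table 3) | Baseline window (Table 2) | Guaranteed look-back |
|---|---|---|---|
| Peripheral neuropathy | 30 days | MM diagnosis to day −1 | 180 days |
| Hepatitis B, hepatitis C | 60 days | MM diagnosis to day −1 (within any infection) | 180 days |
| Renal failure | 60 days | MM diagnosis to day −1 | 180 days |

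**2. Are the codes chronic?** The neuropathy list in Annex 2 includes E11.40 and E11.42. Annex 2 also places E11.4x under diabetes with chronic complications, a Charlson component. The hepatitis lists include B18.0, B18.1 and B18.2, and B18.x is also a Charlson mild-liver-disease code. Annex 2 as shown has no list named renal failure, so the chronic share of that variable cannot be judged.

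**3. A worked patient.** Suppose MM was diagnosed well before index, E11.42 is billed on day −90 and again after index, and no neuropathy code falls in the last 30 days. Table 2 reports baseline neuropathy. The CCI, assessed over 180 days, scores diabetes with chronic complications. The adverse-event table counts incident neuropathy.

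**4. Size under assumptions.** The documents do not give the mean gap g between claims carrying the diagnosis. Assume random (Poisson) coding with g = 60 to 120 days.

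P(existing case has no code in a washout of W days) = exp(−W/g):

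- W = 30: exp(−30/60) = 0.607; exp(−30/120) = 0.779
- W = 60: exp(−60/60) = 0.368; exp(−60/120) = 0.607
- W = 180: exp(−180/60) = 0.050; exp(−180/120) = 0.223

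So 61–78%, 37–61% and 5–22% of existing cases pass washouts of 30, 60 and 180 days.

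A false incident case also needs a code in follow-up. For 90 days after index, P = 1 − exp(−90/g), which is 0.777 at g = 60 and 0.528 at g = 120. The products are:

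| Washout | g = 60 | g = 120 |
|---|---|---|
| 30 days | 0.607 × 0.777 = 47% | 0.779 × 0.528 = 41% |
| 60 days | 0.368 × 0.777 = 29% | 0.607 × 0.528 = 32% |
| 180 days | 0.050 × 0.777 = 4% | 0.223 × 0.528 = 12% |

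If 40% of the cohort had prior neuropathy (assumed), the falsely incident share with a 30-day washout is 0.40 × 0.41 to 0.40 × 0.47, or 16–19% of the cohort. The ceiling, if every missed case were coded again in follow-up, is 0.40 × 0.607 to 0.40 × 0.779, or 24–31%.

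**5. Sensitivity.** The share passing washouts of 30 / 60 / 180 days is 37% / 14% / 0.2% at g = 30, 85% / 72% / 37% at g = 180 and 92% / 85% / 61% at g = 365. With 20% prevalence, g = 90 and 180 days of follow-up, 12.4% of the cohort is falsely incident with a 30-day washout and 2.3% with 180 days. The order of the washouts is the same at every gap; the size is not.

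**The case against.** The strongest reply is that the documents supply neither coding frequency nor prior prevalence, so every percentage above is assumed. Coding at a constant rate is also doubtful just before a new therapy starts, when visits may cluster and prior disease is more likely to be picked up. This stands. It limits what can be said about size, but not the direction of the bias or the conflict between windows.

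Four stronger readings are tempting, and the documents do not support them:

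- A reader might infer that incidence for these conditions will consist mainly of old disease. That needs the true new-onset rate, which is not given. The neuropathy list also holds symptom codes (R20.x, M79.2) and the hepatitis lists hold acute codes (B16.x, B17.1x), so some incident cases may be genuinely new.
- A reader might take 24–31% as the expected error. It omits the need for a code in follow-up, which ends 14 or 90 days after the last administration and is subject to censoring.
- A reader might put renal failure on the same footing as neuropathy and hepatitis. Without a code list in Annex 2 as shown, that cannot be established.
- A reader might expect a longer washout to shrink the number at risk. Section 9.7.6 divides by the whole cohort, so as written only the numerator would fall.

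It is also fair that Table 2 shows baseline neuropathy and renal failure, so a careful reader has some context. Hepatitis B and C appear there only within the infection composite. The analysis serves Exploratory Objective 1, makes no formal comparison, and the protocol does not call incident events treatment-emergent. These points lower the stakes. They do not explain why one patient should be a baseline case in one table and an incident case in another. Nor can the phrase about baseline in the incidence formula be relied on to import the longer window, because the same section sends the reader to Table 3 for the washout length.

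**Conclusion.** The point holds as a design weakness in an exploratory safety measure. As written, the protocol can report one patient's long-standing neuropathy or hepatitis both as a baseline condition and as an incident event, and this biases incidence upward.

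Under random coding with a mean gap of 60–120 days and 90 days of follow-up, the false-incident share of existing cases falls from 41–47% (30 days) or 29–32% (60 days) to 4–12% with 180 days. The 16–19% of the cohort for neuropathy rests additionally on the assumed 40% prevalence. The case is firmest for neuropathy and hepatitis B/C, and conditional for renal failure. Short washouts remain reasonable for acute, recurrent events.

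**What to change.** - For peripheral neuropathy, hepatitis B and hepatitis C, set the incidence washout in Table 3 to at least the full 180-day look-back, or to the Table 2 window (MM diagnosis to day −1). The second option makes the baseline and adverse-event tables agree and catches more prior disease where coding is sparse.
- Give the code list for renal failure, and apply the same rule to the extent that it contains chronic codes.
- Keep the short washouts for acute events such as pyrexia, nausea and acute infections.
- State in Section 9.9 that some misclassification remains, because 180 days does not remove it when claims are far apart.

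The cost is a footnote change and a re-run on data already required. There will be fewer incident cases for these conditions, and new worsening in patients with prior disease will appear only in the prevalence figure. Because the denominator in Section 9.7.6 is the whole cohort, patients removed by the longer washout would still be counted there; the revised text should say whether that is intended.
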